5.5 Efficacy Analysis

5.5.1 General Approach

Blinded Phase:

The primary analyses will use the ITT analysis set. Further analyses using the PP analysis set will also be performed for the primary endpoint and secondary endpoints where specified in the sections below.

The primary null hypothesis is:

- Following 16 weeks of treatment there is no difference in effect between the 25 mg/kg/day GWP42003-P treatment arm and the placebo treatment arm in terms of the change in number of TSC-associated seizures during the treatment period compared to baseline.

The null hypothesis will be rejected if there is statistical evidence of a difference between the treatment arms at the α -level of 0.05 for the primary endpoint.

Statistical hypothesis testing will be performed on the primary endpoint and other endpoints as appropriate. Each endpoint, including the primary will have 2 comparisons against placebo (25 mg/kg/day GWP42003-P vs. placebo and 50 mg/kg/day GWP42003-P vs. placebo). Also, 3 key secondary endpoints have been defined.

The primary and key secondary endpoints will be tested with their Type I error controlled by use of a hierarchical gate-keeping procedure, in the sequence given in Table 3. One must reject the null hypothesis of an endpoint at the level of 0.05 (2-sided) to test the hypothesis of the subsequent endpoint in the sequence at the level of 0.05 (2-sided). If a null hypothesis is not rejected then testing will stop and all subsequent analyses will be declared not statistically significant.

Table 3 Hierarchy for Analysis

Test	Endpoint	Treatment Comparison
1	Primary endpoint	25 mg/kg/day GWP42003-P vs. Placebo
2	1 st key secondary endpoint	25 mg/kg/day GWP42003-P vs. Placebo
3	Primary endpoint	50 mg/kg/day GWP42003-P vs. Placebo
4	1 st key secondary endpoint	50 mg/kg/day GWP42003-P vs. Placebo
5	2 nd key secondary endpoint	25 mg/kg/day GWP42003-P vs. Placebo

6	3 rd key secondary endpoint	25 mg/kg/day GWP42003-P vs. Placebo
7	2 nd key secondary endpoint	50 mg/kg/day GWP42003-P vs. Placebo
8	3 rd key secondary endpoint	50 mg/kg/day GWP42003-P vs. Placebo

All statistical tests will be 2-sided and use the 5% significance level.

The assumptions of normality and homogeneity of variance, for endpoints analyzed using parametric tests, will be checked where appropriate via examination of residual plots as well as computation of summary statistics for normality using the Shapiro-Wilk statistical test. If assumptions are violated then alternative non-parametric techniques will be used. In this instance the original parametric tests will be presented as a sensitivity analysis.

Open-label Extension:

All endpoints will be summarized on the OLE safety analysis set, unless specified otherwise.

Endpoints will be summarized by treatment received during the double-blind phase (GWP42003-P or Placebo, i.e. not split by dose) and overall.

For seizure endpoints, the OLE treatment phase will be split into 12 week periods, for example:

- OLE Week 1 (OLE Day 1) to OLE Week 12 (Day 84)
- OLE Week 13 (OLE Day 85) to OLE Week 24 (OLE Day 168)
- OLE Week 25 (OLE Day 169) to OLE Week 36 (OLE Day 252)
- OLE Week 37 (OLE Day 253) to OLE Week 48 (OLE Day 336)
- OLE Week 49 (OLE Day 337) to OLE Week 60 (OLE Day 420)
- Etc.

In addition, seizure data will be presented for the full OLE treatment phase as well as the last 12 weeks of the OLE treatment phase (see Section 5.1.3.3).

5.5.2 Primary Efficacy Endpoint

Blinded Phase:

The primary endpoint is the change in number of TSC-associated seizures (see Section 5.1.3.7) during the treatment period (see Section 5.1.3.4) compared to baseline period (see Section 5.1.3.1) in patients taking GWP42003-P compared with placebo.

The primary endpoint will be analyzed using a negative binomial regression model with the total number of TSC-associated seizures during the baseline period and treatment period as the response variables.

A mixed effect model with repeated measures will be performed modelling the observed total number of TSC-associated seizures in the baseline period and treatment period implemented within the framework of general linear models using the negative binomial response distribution. The model will include stratified age group (1–6 years, 7–11 years, 12–17 years and 18–65 years), time, treatment arm and treatment arm by time interaction as fixed effects and patient as a random effect. The log transformed number of days in which seizure data were reported will be included as an offset. The time variable corresponds to an indicator for the baseline period and treatment period.

The GLIMMIX procedure in SAS will be utilized to perform the analysis with the option `maxopt=300` applied. If the model fails to converge, then the statement `'nloptions tech=nr ridge;'` will be added. If convergence is still not achieved, then `'method=laplace'` will be utilized. However, if convergence is still not possible, then the model will be changed to utilize the log normal response distribution (log rate model). If the log rate model is required and there are patients with no seizures during the baseline or treatment period then all patients will have their baseline and treatment period seizure count adjusted by adding a value of 1.

The estimated least squares mean seizure rate for each period and the estimated ratio of least squares means for treatment period to baseline period and 95% confidence intervals (CIs) will be presented for each treatment arm. In addition, the estimated ratio of each GWP42003-P arm to placebo and 95% CIs will be presented along with the p-value testing the null hypothesis that this ratio is 1.

For each ratio and upper and lower bound of the 95% CI, the percentage reduction will also be presented, calculated as:

$$[1 - (X \div Y)] \times 100\%$$

Where X corresponds to the treatment period estimate, or GWP42003-P ratio, and Y corresponds to the baseline period estimate, or placebo arm ratio.

Primary efficacy analysis will be performed using the ITT analysis set.

TSC-associated seizure frequency (28-day average) and percentage change in seizure frequency will also be presented using summary statistics. Percentage change from baseline in TSC-associated seizure frequency will be calculated as:

$$((\text{Frequency during the treatment period} - \text{Frequency during baseline}) \div \text{Frequency during baseline}) \times 100$$

The frequency during each period will be based on 28 day averages and calculated as:

$$(\text{Number of seizures in the period} \div \text{Number of reported days in IVRS in the period}) \times 28$$

For the TSC-associated seizure endpoints only, if patients are randomized with no TSC-associated seizures during the baseline period then the percentage change from baseline will be calculated as:

$$(\text{Frequency during the treatment period} + 1) \times 100$$

Open-label Extension:

The primary endpoint for the OLE is the safety of GWP42003-P, evaluated by assessing the incidence, type and severity of AEs. Data will be presented as per Section 5.6.2.

However, percentage change from baseline in TSC-associated seizure frequency is considered a key secondary endpoint for the OLE.

In the OLE, seizures are recorded on a weekly basis rather than daily. Caregivers/patients are expected to call the IVRS system to record the number of seizure subtypes experienced every 7 days during the OLE. TSC-associated seizure frequency per 28 days will be calculated for each of the periods described in Section 5.5.1. All calls that take place during the period in question will contribute to the calculation of the average number of seizures per day in that period only.

The average number of seizures per day in the period will be calculated as the average of:

$$\text{Number of seizures reported} \div \text{Number of days since last IVRS call}$$

The number of days since the last call will be calculated as follows, and is dependent on whether the call took place <7, 7 or >7 days after the previous call (or after the date of OLE Day 1 in the case of the first call in the first period):

- If the call takes place exactly 7 days after the previous call, then the number of days since the last call will be 7.
- If the call takes place <7 days after the previous call, then the number of days since the last call will be calculated as:
$$(\text{Date of current call} - \text{date of previous call}) + 1$$
- If the call takes place >7 days after the previous call, then the number of days since the last call will be 7.

Summary statistics will be presented for raw seizure frequencies and percentage change from baseline (from the blinded phase).

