5.1.3 Definitions

5.1.3.1 Baseline

For clinic visit based endpoints, baseline is defined as the last record or measure collected prior to the first dose of IMP.

For IVRS based endpoints, baseline will include all available data from the day of Visit 2 to Day 1 of the blinded phase.

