The responses above are based on comparison with a brief description of the patient's overall condition used as a memory aid from Visit 3.

Each response will be coded with a score from 1 to 7, where 1 = Very Much Improved, and 7 = Very Much Worse.

The SGIC and CGIC response/score, recorded at each visit, will be summarized separately, on both a categorical and continuous scale, by treatment arm.

It is anticipated that only a small percentage of patients will complete the subject version of the questionnaire. Hence, no analyses will be performed for the SGIC.

A combined score will be used as the primary analysis for this endpoint. The combined score will be defined as follows:

- If both a CGIC and SGIC are completed then the CGIC will be used.
- If only a CGIC is completed then the CGIC will be used.
- If only a SGIC is completed then the SGIC will be used.

The score at the end of treatment visit and last visit (if different to the end of treatment) will be analyzed using ordinal logistic regression. Proportional odds modelling will be carried out by including treatment arm as a factor. The estimated odds ratio (GWP42003-P vs. placebo), 95% CI for the odds ratio, and the p-value testing the null hypothesis that the odds ratio is equal to 1, will be presented. Analysis performed at the last visit will be considered the primary analysis for this endpoint, with the analysis at the end of treatment visit considered a sensitivity analysis.

Should the proportional odds assumption not hold, i.e. if the p-value for the score test for proportional odds assumption is <0.05 , then, as a sensitivity analysis, the scores will also be analyzed using a Cochran-Armitage trend test. This will be presented together with the results of the ordinal logistic regression.

Since this analysis uses a combination of caregiver and subject ratings, a sensitivity analysis will be performed using only the CGIC score and using the same analyses as above.

The analysis will be performed on the ITT analysis set and repeated on the PP analysis set.

Open-label Extension:

Descriptive summaries described above for the blinded phase will be repeated for OLE visits.

5.5.3.1.3 3rd Key Secondary Endpoint: Total Seizures

Blinded Phase:

Summaries and analyses of total seizures (see Section 5.1.3.9) will be performed as per the primary endpoint (Section 5.5.2).

The analysis will be performed on the ITT analysis set and repeated on the PP analysis set.

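### The primary count model gives each arm its own baseline rate: a valid test, but less precise than one with a common baseline

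*SAP*

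**What the plan says.** SAP section 5.5.2 models two counts per patient in one "negative binomial regression model with the total number of TSC-associated seizures during the baseline period and treatment period as the response variables". Besides age group, the linear predictor holds "time, treatment arm and treatment arm by time interaction as fixed effects and patient as a random effect". Period has two levels: "The time variable corresponds to an indicator for the baseline period and treatment period". Exposure enters on the log scale: "The log transformed number of days in which seizure data were reported will be included as an offset".

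For the confirmatory comparison, "the estimated ratio of each GWP42003-P arm to placebo and 95% CIs will be presented along with the p-value". The definition used for the percentage reduction shows what is being compared: "Where X corresponds to the treatment period estimate, or GWP42003-P ratio, and Y corresponds to the baseline period estimate, or placebo arm ratio". The quantity tested is thus the active arm's treatment-to-baseline ratio divided by placebo's. The log-normal fallback changes the response distribution only.

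Section 5.5.3.1.3 carries the model over to the third key secondary endpoint: "Summaries and analyses of total seizures (see Section 5.1.3.9) will be performed as per the primary endpoint". It therefore decides Tests 1, 3, 6 and 8 of Table 3 in section 5.5.1.

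For this endpoint, baseline seizure frequency is a covariate only in three of the sensitivity analyses in section 5.5.2.1 (rank, log-transformed and percentage-change ANCOVA). None of these feeds the testing sequence.

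**The concern.** With two periods and a free arm effect, every arm-by-period mean is free, and the arm main effect is simply the arm difference at baseline. Under randomization that difference has expectation zero, so the model spends information estimating chance. The arm-by-period term becomes a log-scale change score, with the baseline slope fixed at 1 in effect.

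There are two consequences. First, the standard error is larger than the data already collected would allow. Second, randomization is stratified by age only (section 3.1), so baseline seizure frequency can differ between arms by chance. Regression to the mean then carries part of that difference into the ratio.

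The sequence in section 5.5.1 is strictly ordered, so a loss of power at Test 1 puts every later claim at risk.

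**Working it through.** **Inputs from the SAP.** Section 3.2: 70 per arm with pooled placebo, mean reductions of 15% and 50%, SD 60%, two-sided 5%. Section 5.1.3.1: "baseline will include all available data from the day of Visit 2 to Day 1 of the blinded phase", about 28 days. Section 5.1.3.4: treatment period from Day 1 to Day 113.

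**Assumed inputs.** The SAP gives neither rho nor the SD of log seizure rates. I take rho from 0.5 to 0.9 and, where needed, a log-rate SD of 1.

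**Step 1, the plan's own figure.** Noether's formula for the Mann-Whitney-Wilcoxon test has p = Phi(35/(60 x sqrt 2)) = 0.660. The total is (1.960 + 1.282)^2 / (12 x 0.25 x (0.660 - 0.5)^2) = 136.8, or 68.4 per arm. Power at 70 per arm is 90.6%. The stated 70 per arm and 90% power reproduce. They concern a rank test on percentage change, not the model in section 5.5.2.

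**Step 2, precision.** Assume equal log-scale variance sigma^2 in the two periods.
- Planned contrast, per patient: 2 x sigma^2 x (1 - rho).
- Baseline-adjusted or common-baseline contrast: sigma^2 x (1 - rho^2).
- Variance ratio, planned over adjusted: 2/(1 + rho).

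The effective size is 70 x (1 + rho)/2. A test with 90% power under the adjusted analysis has power Phi(3.242/sqrt(2/(1 + rho)) - 1.960) under the planned one.

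**Step 3, dependence on chance imbalance.** The planned log ratio shifts by about -(1 - rho) per unit of observed log baseline difference (active minus placebo). With log-rate SD 1, one SD of imbalance is sqrt(2/70) = 0.169, so the rate ratio changes by a factor of exp((1 - rho) x 0.169).

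| rho | Variance ratio | SE excess | 70 per arm worth | 90% becomes | Ratio shift at 1 SD imbalance |
|---|---|---|---|---|---|
| 0.5 | 1.33 | 15% | 52.5 | 80.2% | 8.8% |
| 0.7 | 1.18 | 8% | 59.5 | 84.8% | 5.2% |
| 0.8 | 1.11 | 5% | 63.0 | 86.8% | 3.4% |
| 0.9 | 1.05 | 3% | 66.5 | 88.5% | 1.7% |

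**Step 4, simulation of the count model.** Two arms of 70, with 28 and 113 reported days, a negative binomial response with random intercept SD 1, a true rate ratio of 0.7 and 400 runs per row. All scenario values other than the arm size and period lengths are assumptions. Each data set was fitted with and without arm-specific baselines.

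| Median per 28 days, dispersion | rho | Variance ratio, planned/common | Slope on imbalance, planned | Slope, common baseline |
|---|---|---|---|---|
| 56, 1.0 | 0.39 | 1.49 | -0.63 | -0.06 |
| 56, 0.5 | 0.60 | 1.25 | -0.39 | -0.01 |
| 56, 0.25 | 0.75 | 1.10 | -0.21 | 0.03 |
| 56, 0.1 | 0.87 | 1.14 | -0.17 | -0.06 |
| 20, 0.25 | 0.74 | 1.08 | -0.20 | 0.07 |

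The formulas in Steps 2 and 3 are borne out to within what 400 runs can show. A separate set of 500 to 600 runs per case put the common-baseline model's type I error at 4.5% to 5.2%. Its SE reductions were 6.2% (0.1285 to 0.1205), 4.4% (0.1341 to 0.1282) and 2.4% (0.0846 to 0.0826).

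**The case against.** The SAP contradicts nothing here. Its endpoint and null hypothesis are framed as change from baseline compared between arms, and the planned ratio tests exactly that. Arm-specific baselines also supply directly the per-arm period ratios that section 5.5.2 asks for. Baseline is used, as each patient's own reference, so it would be wrong to infer that the model ignores it. Any effect of imbalance should show in the covariate-adjusted sensitivity analyses.

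The loss may also be small. If the section 3.2 reductions are read as a rate ratio of 0.50/0.85 = 0.59 (an assumption), the SEs from the second set of simulations give power of 98.5% against 99.3%, 97.7% against 98.5%, and about 100% for both. The gain is then under one point. A smaller true effect or a lower rho would make it larger, and the SAP settles neither.

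All of this stands, and it limits the weight of the point. What remains is that sensitivity analyses cannot recover power lost in an ordered confirmatory sequence, and that the gain requires no further patients or data.

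**Conclusion.** The point holds as one of efficiency and of accuracy given the baseline imbalance actually observed. Over assumed rho of 0.5 to 0.9, the planned contrast carries 33% to 5% more variance than necessary. At rho of 0.8 or more the SE excess is about 5% or less. These figures rest on the assumed rho and on equal log-scale variances; the simulations support them under further assumed inputs.

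A reader might infer three stronger things that the document does not support:
- **That the primary estimate is biased.** Over repeated randomization it is essentially unbiased. The shift is conditional on the observed imbalance and can favour either arm.
- **That the test is invalid.** Nothing in this structure inflates its type I error.
- **That the stated 90% power is overstated for this reason.** Section 3.2 rests on a Mann-Whitney-Wilcoxon test, and its figures reproduce.

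**What to change.** For the primary endpoint and total seizures, drop the arm main effect so that all arms share one baseline rate. The fixed effects become age group, period and arm by period, with the same random patient effect and offset. Keep the present model as a sensitivity analysis.

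The coding should be stated. Use one indicator per active arm, equal to 1 in the treatment period only. If arm and period are class variables, deleting the arm term while keeping the full interaction leaves all cell means free and changes nothing.

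A log-baseline covariate should not be offered as an equivalent. It is undefined for zero baseline counts, which section 5.5.2 anticipates, and in a negative binomial model the two approaches are not the same. The joint model needs no added constant.

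Costs: the per-arm treatment-to-baseline ratios would refer to the common baseline. The analyses that repeat the primary model (sections 5.5.2.1, 5.5.2.1.1, 5.5.3.2.3, 5.5.4.1 and 5.5.4.2) need matching wording, and the subgroup models in section 5.5.5 need respecifying because they add effect-by-arm terms.

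The change must be made before unblinding. The post-hoc addendum already reports withdrawal by arm (its section 2.3.3), which suggests that point has passed. If so, the common-baseline analysis can only be supportive.

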3. INVESTIGATIONAL PLAN

3.1 Trial Design

This multicenter trial consists of a randomized, placebo-controlled, double-blind phase followed by an open-label extension (OLE) phase.

Blinded Phase:

The blinded phase of the trial is a randomized, double-blind, parallel-group, 16-week comparison of two doses of GWP42003-P vs. placebo. Patients will complete a 1-week screening period and a 4-week baseline period before they are randomized to receive either 25 mg/kg/day GWP42003-P, 50 mg/kg/day GWP42003 P or placebo. Randomization will be stratified by age according to the following ranges: 1–6, 7–11, 12–17 years and 18–65 years. Patients will begin a 4-week dose escalation period, titrating up to their assigned dose, before continuing on a stable dose of blinded Investigational Medicinal Product (IMP) for 12 weeks.

Dose escalation for each patient is subject to the investigator's assessment of safety and tolerability. If a dose becomes poorly tolerated, the investigator may consider temporarily or permanently reducing the dose for the remainder of the trial.

Following completion of the blinded phase, patients will be invited to continue to receive GWP42003-P in an OLE.

Those patients opting not to enter the OLE will complete a 10-day taper period (down-titrating 10% per day for 10 days).

Open-label Extension Transition:

In order to maintain consistent exposure to IMP and maintain the integrity of the blind, patients will enter a 2-week blinded transition to the OLE. OLE IMP will be titrated up to 25 mg/kg/day whilst blinded IMP is simultaneously tapered down to zero. All patients will complete the transition and enter the OLE taking 25 mg/kg/day GWP42003-P:

- Patients from the placebo arm will titrate up to 25 mg/kg/day GWP42003-P.
- Patients from the 25 mg/kg/day GWP42003-P arm will continue to take 25 mg/kg/day GWP42003-P.
- Patients from the 50 mg/kg/day GWP42003-P arm will taper down (10% per day) to 25 mg/kg/day GWP42003-P.

Open-label Extension:

The OLE consists of a 3-week titration period followed by a maintenance period and a 10-day taper period. The initial OLE period will last for a maximum of 1 year.

Following titration according to the titration schedule, patients will continue with their optimal GWP42003-P dose. However, investigators may decrease the dose if a patient experiences intolerance, or increase the dose to a maximum of 50 mg/kg/day if required for better seizure control, until the optimal dose is found.

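### The primary model lists the age stratifier only as a main effect, so it has almost no influence on the arm-by-time test used in Tests 1, 3, 6 and 8 (minor loss of efficiency)

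*SAP*

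**What the plan says.** Section 3.1: "Randomization will be stratified by age according to the following ranges" 1–6, 7–11, 12–17 and 18–65 years.

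Section 5.5.2 fits a negative binomial mixed model to two counts per patient. "The model will include stratified age group", followed by "time, treatment arm and treatment arm by time interaction as fixed effects and patient as a random effect". There is no age-by-time term. "The time variable corresponds to an indicator for the baseline period and treatment period", so time has two levels. For inference, "the estimated ratio of each GWP42003-P arm to placebo and 95% CIs will be presented along with the p-value" testing whether that ratio is 1. The accompanying definition reads "Where X corresponds to the treatment period estimate, or GWP42003-P ratio, and Y corresponds to the baseline period estimate, or placebo arm ratio". The tested quantity is therefore the active arm's treatment-to-baseline ratio divided by placebo's, which is the exponentiated arm-by-time coefficient.

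Table 3 in Section 5.5.1 makes this model Tests 1 and 3 (primary endpoint). Section 5.5.3.1.3 extends it to Tests 6 and 8: "Summaries and analyses of total seizures (see Section 5.1.3.9) will be performed as per the primary endpoint".

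Age is handled differently elsewhere. The responder analysis (Tests 2 and 4, Section 5.5.3.1.1) is a CMH test stratified by age group. Section 5.5.2.1 has rank, log-transformed and percentage-change ANCOVAs with age group as a covariate, as sensitivity analyses. Section 5.5.5 fits the primary model with each effect modifier, including age group, interacted with time, arm and both.

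**The concern.** A reader who sees the stratification factor among the fixed effects will take the primary test as adjusted for it. In a model where baseline is itself a response, a covariate adjusts the treatment comparison only if it is allowed to act on change, that is, through its interaction with time. A main effect acts on level, which the patient random effect already carries.

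Stratified randomization balances age across arms, so the true sampling variance of the treatment contrast excludes between-age variation in change. A model that leaves this variation in the residual reports a standard error that is too large. Test 1 opens a fixed sequence, so lost precision there bears on every later claim.

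**Working it through.** **1. The planned sample size.** Inputs from Section 3.2: reductions of 15% and 50%, SD 60%, 70 per arm, two-sided 5% Wilcoxon test, 90% power.
- Noether's formula: p = Φ(35/(60√2)) = 0.660.
- n per arm = (1.960 + 1.282)² / [2 × 12 × 0.25 × (0.160)²] = 68.4, so 69.
- At 70 per arm: Φ(√(140 × 3) × 0.160 − 1.96) = Φ(3.279 − 1.96) = 90.6%.

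The SAP's figure is reproduced.

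**2. Why the age term cancels.** For patient i in period t (0 baseline, 1 treatment), the Section 5.5.2 log rate is

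η(i,t) = μ + α(age) + γ(arm) + βt + δ(arm)t + b(i).

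So η(i,1) − η(i,0) = β + δ(arm). The age effect α and the patient effect b both drop out. Only an age-by-time term would remain in the difference.

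**3. Linear check (log-rate model, both periods observed).** Arm-by-time estimate (SE) in two simulated data sets:

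| Model | Set 1 | Set 2 |
|---|---|---|
| no age | −0.63878 (0.11822) | −0.46511 (0.12557) |
| age main effect | −0.63878 (0.11822) | −0.46511 (0.12557) |
| plus age × time | −0.64558 (0.11548) | −0.43907 (0.12264) |

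The main effect changes nothing at the precision shown.

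**4. Negative binomial model, effect of the age main effect.** The cancellation is now approximate. Two simulations were run; all their parameters are assumptions.
- Simulation A: 70 per arm, dispersion 0.25, patient SD 1.0, offsets log 28 and log 113, 500–600 runs. The log rate ratio moved by 0.001–0.003 on average and the SE by under 0.0001.
- Simulation B: 208 patients, dispersion 0.35, patient SD 0.9, 2 seizures a day, 600 runs per case. The SE fell by 0.2–0.9%. The estimate moved by 0.009–0.015 on average (0.073 at most in a single run), against SEs of 0.154–0.171, so by less than a tenth of an SE on average.

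**5. What age by time would add (Simulation A, effect tuned to about 90% power).**

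| SD of age-group log changes | SE planned → with age × time | SE cut | Power planned → with age × time |
|---|---|---|---|
| 0 | 0.1285 → 0.1272 | 1.0% | 89.8% vs 90.0% (no loss) |
| 0.2 | 0.1326 → 0.1271 | 4.1% | 89.7% → 90.8% |
| 0.3 | 0.1378 → 0.1272 | 7.7% | 88.5% → 90.7% |

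At SD 0.3 the planned SE exceeds the true sampling SD by 0.1378/0.1316 − 1 = 4.7%.

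**6. Direction of the error.** Simulation B under the null, with age SD 0.45: the planned model has mean SE 0.171 against true SD 0.160 and rejects 4.2%. With age × time the figures are 0.153, 0.156 and 5.3%. The Monte Carlo error is about 0.9 points. Neither shows inflation.

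**7. Analytic check.** Let R² be the share of the variance of change explained by age (assumed), and s = √(1 − R²). Planned size is 2[1 − Φ(1.96/s)]. Planned power is Φ((3.279 − 1.96)/s). Power with age × time is Φ(3.279/s − 1.96).

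| R² | Planned size | Planned power | Power with age × time |
|---|---|---|---|
| 0 | 5.0% | 90.6% | 90.6% |
| 2% | 4.8% | 90.9% | 91.2% |
| 5% | 4.4% | 91.2% | 92.0% |
| 10% | 3.9% | 91.8% | 93.3% |
| 20% | 2.8% | 93.0% | 95.6% |

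**8. Dependence on the true effect.** Reading Section 3.2 as a rate ratio of 0.50/0.85 = 0.588 (an assumption; log = −0.531) and using Simulation A's SEs:
- SD 0.2: Φ(0.531/0.1326 − 1.96) = 97.9% against Φ(0.531/0.1271 − 1.96) = 98.7%.
- SD 0.3: Φ((0.531 − 1.96 × 0.1378)/0.1316) = 97.6% against Φ(0.531/0.1272 − 1.96) = 98.7%.

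The loss is then 0.7–1.0 point. Where power is low it is larger: Simulation B at a ratio of 0.68 and age SD 0.27 gave 65.5% against 69.2%.

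**The case against.** The strongest reply is that this is a matter of efficiency, not validity, and a small one. That stands. A reader might infer that the primary test is biased or its error rate inflated because the stratifier is not used. The SAP supports neither, since omitting a balanced stratifier makes the test conservative. A reader might also infer that the age term does nothing at all. That is exact only in the log-rate fallback with both periods observed. In the negative binomial model it holds approximately, and the term still enters the reported least squares mean rates.

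The size is also open to challenge. The SAP gives nothing to show that change differs by age. The power differences of 1.1 and 2.2 points rest on assumed age spreads, and each power figure has a Monte Carlo error of about 1.2–1.3 points. About 1 percentage point of the SE cut appears even with no age effect. In Simulation B the mean SE of the enlarged model lies slightly below its true SD (0.153 against 0.156). The simulations used quadrature, whereas Section 5.5.2 turns to the Laplace method only after two failed attempts.

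Age-adjusted results for the primary endpoint are also prespecified in Sections 5.5.2.1 and 5.5.5. This softens the point, but those analyses are supportive and do not decide Tests 1, 3, 6 or 8.

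Finally, adding the term everywhere is not free. The seizure-type models in Section 5.5.4.2 exclude patients without that type at baseline and are repeated by 4-week period, so age cells may be thin. This limits the fix.

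**Conclusion.** The point holds as a minor one. It follows from the model statement itself that the age main effect has practically no influence on the arm-by-time test. The confirmatory count analyses therefore do not make effective use of the factor on which the trial is randomized, while the responder tests do.

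The consequence is conditional. With age-group SDs of 0.2–0.3 in log change, the SE is about 4–8% larger than with age by time, and power near 90% is about 1–2 points lower. The loss is smaller if the true effect is larger, and nil if change does not depend on age. These sizes rest on assumed age spread, dispersion and patient variance. The direction (conservative, unbiased) does not depend on the particular values chosen.

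**What to change.** In Section 5.5.2, add the interaction of stratified age group with time, giving fixed effects of age group, time, arm, age group by time and arm by time. Report each arm's period ratio averaged over the observed age mix. Apply this to the primary and total-seizure analyses and to their PP, period and imputation repeats. Keep the simpler model for individual seizure types or 4-week periods where age cells are sparse, and state that rule in advance.

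The cost is 3 degrees of freedom with about 210 patients, a slightly higher risk of reaching the later convergence steps, and SAP wording. No new data are needed. The addendum is post hoc, so if the main SAP can no longer be changed, report the age-by-time model as a labelled sensitivity analysis and do not describe the primary test as adjusted for the stratification factor.
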